1.0 OVERVIEW OF STUDY DESIGN

The FC-9 study is designed as a phase II, open label, single arm study of the dual immune checkpoint blockade with the combination of durvalumab and tremelimumab following hypofractionated palliative radiation in patients with microsatellite stable (MSS) metastatic colorectal cancer (mCRC) who have progressed on chemotherapy. The primary aim is to determine the anti-tumor efficacy of the dual immune checkpoint blockade with durvalumab plus tremelimumab. The secondary aims are to determine the clinical benefit rate, duration of response, tolerability and correlates of response. Tumor response at unirradiated target lesions will be measured at baseline and every 2 cycles using RECIST 1.1.

[figure not shown]
Following three doses of hypofractionated palliative radiation (Days -2, -1, and Day 0 prior to Cycle 1), patients will receive the combination of tremelimumab (75 mg IV infusion) and durvalumab (1500 mg IV infusion) on Day 1 for 4 cycles. Beginning with Cycle 5 through Cycle 24, patients will receive durvalumab alone (1500 mg/IV infusion) on Day 1 of each 28 day cycle.

Toxicity will be graded according to the National Cancer Institute (NCI) Common Terminology Criteria for Adverse Events version 4.0.

The sample size will be between 12 and 21 evaluable patients. Patients who complete both Cycle 1 and Cycle 2, and undergo the first restaging scan after Cycle 2 for the determination of tumor response will be determined evaluable. Non-evaluable patients will be replaced. Twelve evaluable patients will be treated in the first stage of the study. If there are no responses among the 12 evaluable patients, the study will be terminated. If the study goes on to the second stage, a total of 21 evaluable patients will be studied. If the total number responding is less than or equal to 2, the combination will be rejected. If 3 or more responses are observed after the second stage of the study, the combination will be considered for further study.

Submission of tumor tissue and blood samples for FC-9 correlative science studies will be a study requirement for all patients. Requirements will include archived tumor samples from the diagnostic biopsy; additional biopsies of fresh tissue from an accessible lesion prior to radiation therapy and after 2 cycles of study therapy; and blood sample collections.

Figure 1
FC-9 Schema

‡Hypo-fractionated stereotactic body radiation therapy (SBRT)

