2.9 Translational opportunities

Pre-clinical and clinical data suggest that combination of immune checkpoint inhibitors targeting non-overlapping pathways such as durvalumab and tremelimumab may induce synergistic effect leading to improved tumor response in comparison to monotherapy with either agent alone. We hypothesize that the combination of radiation and dual immune checkpoint blockade with durvalumab plus tremelimumab may have synergistic effect on effector T cell activation ([Pardoll 2012](#)).

This study serves as a platform allowing for detailed assessment of the mechanisms of immune stimulation, predictive markers of response or resistance and rational development of the next generation of combination immunomodulatory interventions ([Taube 2014](#), [Topalian 2012](#)). Samples will be collected that may be used in post-hoc analyses including but, not limited to:

- peripheral lymphocytes analysis for immune cell gene expression and quantitative changes of lymphocyte subpopulation and immune-related cells.
- collection of tumor tissues from unirradiated tumor sites prior to radiation and after two cycles of therapy for further analysis of immune response in tumor.
- analysis of gene expression related to immune checkpoint pathways.
- analysis of frequency of mutation-associated neoantigens in tumor tissues.

3.0 **STUDY AIMS AND ENDPOINTS**

3.1 **Primary aim and endpoint**

Aim: To determine the efficacy of the dual immune checkpoint blockade with durvalumab plus tremelimumab following a small dose of hypofractionated palliative radiation in patients with MSS mCRC who have progressed on chemotherapy.

Endpoint: Overall objective response rate (ORR) as measured by RECIST 1.1 criteria.

3.2 **Secondary aims and endpoints**

3.2.1 ***Clinical benefit rate***

Aim: To determine objective tumor decrease and stable disease (SD) at 16 weeks.

Endpoint: Measurement of disease status by continuous tumor measurement (any partial response [PR], any complete response [CR] and SD at 16 weeks).

3.2.2 ***Duration of response***

Aim: To determine the duration of response of mCRC to study therapy.

Endpoint: Measurement of time from study entry until documentation of progression as determined by RECIST 1.1.

3.2.3 ***Safety and Toxicity***

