4.0 PATIENT ELIGIBILITY AND INELIGIBILITY

4.1 Conditions for patient eligibility

A patient cannot be considered eligible for this study unless all of the following conditions are met:

- 4.1.1 The patient must have consented to participate and, prior to beginning specific study procedures, must have signed and dated an appropriate IRB-approved consent form that conforms to federal and institutional guidelines for study treatment and for submission of tumor and blood samples as required by FC-9 correlative science studies (see [Section 6.0](#)).
- 4.1.2 Patients must be ≥ 18 years old.
- 4.1.3 The ECOG performance status must be 0 or 1 (see [Appendix A](#)).
- 4.1.4 There must be histologic confirmation of a diagnosis of colorectal adenocarcinoma.
- 4.1.5 The tumor must have been determined to be microsatellite stable (MSS).
- 4.1.6 There must be documentation by PET/CT scan, CT scan, or MRI, that the patient has evidence of measurable metastatic disease per RECIST 1.1.
- 4.1.7 Patients must have an accessible metastatic lesion for pretreatment core biopsy.
- 4.1.8 Unless either drug is medically contraindicated, patients must have received oxaliplatin and irinotecan as part of standard metastatic chemotherapy regimens.
- 4.1.9 The patient must have multiple sites of metastatic disease with at least one lesion amenable to treatment with stereotactic radiation therapy (SBRT) in the lung or liver and at least one lesion not being irradiated and meeting RECIST 1.1. (See [Appendix B](#)).
- 4.1.10 At the time of study entry, blood counts performed within 2 weeks prior to study entry must meet the following criteria:
 - ANC must be $\geq 1500/\text{mm}^3$,
 - Platelet count must be $\geq 100,000/\text{mm}^3$; and
 - Hemoglobin must be ≥ 9 g/dL.
- 4.1.11 The following criteria for evidence of adequate hepatic function performed within 2 weeks prior to study entry must be met:
 - Total bilirubin must be $\leq 1.5 \times \text{ULN}$ (upper limit of normal) for the lab unless the patient has a bilirubin elevation $> 1.5 \times \text{ULN}$ to $3 \times \text{ULN}$ due to Gilbert's disease or similar syndrome involving slow conjugation of bilirubin; *and*
 - AST and ALT must be $\leq 2.5 \times \text{ULN}$ for the lab *with the following exception*: for patients with documented liver metastases, AST and ALT must be $\leq 5 \times \text{ULN}$.

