11.1 Definitions of measurable and non-measurable disease

11.1.1 *Measurable disease:*

Measurable lesions are defined as those that can be accurately measured in at least one dimension (longest diameter to be recorded) as ≥ 20 mm with conventional techniques (PET/CT, CT scan, or MRI) or as ≥ 10 mm with spiral CT scan with 5 mm cuts. All tumor measurements must be recorded in millimeters (or decimal fractions of centimeters). The same method (CT, MRI, or PET/CT) used at baseline should be used at all other tumor measurement time points.

11.1.2 *Non-measurable disease*

All other lesions, including small lesions (longest diameter < 20 mm with conventional techniques or < 10 mm using spiral CT scan with 5 mm cuts) are considered to be non-measurable disease.

11.1.3 *Target lesions*

Up to a maximum of five measurable lesions should be identified as target lesions and recorded and measured at baseline. Target lesions (maximum 2 lesions per organ) should be selected on the basis of their size (lesions with the longest diameter) and their suitability for accurate repeated measurements by CT scan or MRI. A sum of the longest diameter (LD) for all target lesions will be calculated and reported as the baseline sum LD. The baseline sum LD will be used as reference by which to characterize the objective tumor response.

11.1.4 *Non-target lesions*

All sites of disease which are not used as target lesions should be identified as non-target lesions. Location of individual lesions within the liver does not have to be specifically recorded. All sites of non-target lesions must be assessed along with the target lesions.

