11.2 Response criteria

11.2.1 *Evaluation of target lesions*

- *Complete response (CR)*
Disappearance of all target lesions
- *Partial response (PR)*
At least a 30% decrease in the sum of the of LD of target lesions, taking as reference the baseline sum LD

- *Progressive disease (PD)*
At least a 20% increase in the sum of the LD of target lesions, taking as reference the smallest sum LD recorded since baseline or the appearance of one or more new lesions
- *Stable disease (SD)*
Neither sufficient shrinkage to qualify for PR nor sufficient increase to qualify for PD, taking as reference the smallest sum LD since baseline

11.2.2 *Evaluation of non-target lesions*

- *Complete response (CR)*: disappearance of all non-target lesions,
- *Incomplete response/stable disease (SD)*: persistence of one or more non-target lesion(s).
- *Progressive disease (PD)*: Appearance of one or more new lesions and/or unequivocal progression of existing non-target lesions.

11.2.3 *Evaluation of best overall response*

The best overall response is the best response recorded from the start of the treatment until disease progression/recurrence (taking as reference for progressive disease the smallest measurements recorded since the treatment started).

Refer to [Table 8](#) for a summary of the criteria that contribute to the determination of response.

Table 8. Determination of response

Target Lesions	Non-Target Lesions	New Lesions	Overall Response
CR	CR	No	CR
CR	Incomplete response/SD	No	PR
PR	Non-PD	No	PR
SD	Non-PD	No	SD
PD	Any	Yes or No	PD*
Any	PD	Yes or No	PD*
Any	Any	Yes	PD*

*Confirmation of PD in a patient with new lesion(s) or suspected tumor flare is required as outlines in [Sections 11.2.1](#) and [11.2.2](#).

11.3 **Symptomatic deterioration**

Patients with a global deterioration of health status requiring discontinuation of treatment without objective evidence of disease progression at that time should be reported as "symptomatic deterioration." This is also true for "symptomatic deterioration" after therapy is completed. Every effort should be made to document objective progression even after discontinuation of treatment.

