7.1 Primary Analysis of Stage II: Objective Response Rate

The ITT population will be used to test the effects of therapy on ORR. The best overall response is the best response recorded from the start of the treatment until disease progression/recurrence (taking as reference for progressive disease the smallest measurements recorded since the treatment started). Confirmation of complete or partial response IS NOT required.

A summary table presenting % of patients with a best overall response of CR, PR, SD and PD will be made. ORR will be calculated as % of patients with CR or PR at any time during the treatment (including unscheduled assessments). The 95 % confidence interval of the ORR proportion will be reported using exact method based on the binomial distribution (Clopper-Pearson method). The denominator will be the number of patients in the ITT population.

The primary objective of the trial will be reached if at least 3 responses are observed among 21 evaluable patients (14.3%).

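### RECIST 1.1 is the named standard, but Section 11 gives unversioned and internally inconsistent lesion and progression rules, and SAP 7.1 counts unconfirmed responses without saying whether the 5% null does too

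*Combined protocol and SAP*

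**What the plan says.** **The named standard.** Protocol Section 3.1 sets the primary endpoint as "Overall objective response rate (ORR) as measured by RECIST 1.1 criteria". Section 1.0 adds: "Tumor response at unirradiated target lesions will be measured at baseline and every 2 cycles using RECIST 1.1". Section 4.1.6 requires "evidence of measurable metastatic disease per RECIST 1.1", Section 4.1.9 requires at least one unirradiated lesion meeting the same criteria, and footnote e of Table 2 repeats the version for the 2-cycle assessments.

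**The rules as written.** Section 11.0 refers to standard RECIST with no version and declares one exception, the documentation of PD. Then:

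- Section 11.1.1 sets measurability at "20 mm with conventional techniques (PET/CT, CT scan, or MRI") or at 10 mm on spiral CT with 5 mm cuts. Section 11.1.2 makes everything smaller non-measurable.
- Section 11.1.3: "A sum of the longest diameter (LD) for all target lesions will be calculated". It gives no separate rule for any lesion type.
- Section 11.2.1 defines PD as "At least a 20% increase in the sum of the LD of target lesions, taking as reference the smallest sum LD recorded since baseline", or a new lesion. No minimum in millimetres is given.
- The footnote to Table 8 requires PD to be confirmed when there are new lesions or suspected flare, and cites Sections 11.2.1 and 11.2.2. Neither contains a confirmation rule; the only one is in 11.0.

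**Confirmation of response.** The protocol is silent. SAP 7.1 states: "Confirmation of complete or partial response IS NOT required". Protocol Section 14.2 tests 5% against 20% without saying which kind of response either rate refers to.

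**The concern.** The trial is single-arm and open-label, its decision rests on 3 responses in 21 patients, and the documents describe no independent image reading. The plan should therefore leave no doubt about which lesions can be targets, what ends the response window and what counts as a response. Three things are at stake.

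- **Measurability.** Whether a 10–19 mm lesion can be a target depends on how the scan is labelled. A patient entered on such a lesion by MRI could not reach PR, yet would sit in the denominator.
- **Progression.** With no absolute minimum, very small growth in a small target is PD. That bears on clinical benefit rate (CBR), duration of response (DOR) and continuation of treatment.
- **Response.** A single scan at the threshold counts. If the 5% null describes confirmed responses, the type I error of the 3-of-21 rule is higher than stated.

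**Working it through.** **1. Measurability (Section 11.1.1) applied to a 14 mm lesion**

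| Scan label | Threshold | Target? |
|---|---|---|
| Spiral CT, 5 mm cuts | 10 mm | yes |
| CT as a conventional technique | 20 mm | no |
| MRI | 20 mm | no |
| PET/CT | 20 mm | no |

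Table 1 allows PET/CT, CT or MRI at baseline, and the same method must be kept afterwards. Table 8 yields an overall PR only from a CR or PR in target lesions, so a patient with no qualifying target cannot respond. The ORR denominator in SAP 7.1 is the population in SAP 3.3.1: two completed cycles and the first restaging scan. Having a target lesion is not a condition.

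**2. PD and PR in millimetres**

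PD needs growth of 0.20 × nadir sum: 2 mm at 10 mm, 4 mm at 20 mm, 10 mm at 50 mm. PR needs shrinkage of 0.30 × baseline sum: 3 mm at 10 mm. The 10 mm case is possible because 4.1.9 requires only one unirradiated lesion. In general, a floor of d mm would change PD calls only where 0.20 × nadir < d, that is, for nadir sums below 5d.

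PD does not enter the PR rule. It can lower ORR only by closing the best-response window (11.2.3) before a response occurs.

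**3. The plan's own operating characteristics**

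Inputs from Section 14.2: stop if 0 of 12 respond; declare active if at least 3 of 21 respond; p0 = 0.05, p1 = 0.20.

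P(active | p) = Σ over x = 1..12 of Bin(x; 12, p) × P(Y ≥ max(0, 3 − x)), with Y ~ Bin(9, p).

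At p = 0.05:

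- x = 0 (stop): 0.95^12 = 0.5404. Expected N = 12 + 0.4596 × 9 = 16.14.
- x = 1: 0.3413 × P(Y ≥ 2) = 0.3413 × 0.0712 = 0.0243.
- x = 2: 0.0988 × P(Y ≥ 1) = 0.0988 × 0.3698 = 0.0365.
- x ≥ 3: 0.0196.
- Total 0.0804. Stated: 0.080.

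At p = 0.20 the same sum is 0.8033, so β = 0.1967. Stated: 0.197. All the stated figures reproduce.

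**4. Sensitivity to unconfirmed responses**

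Assumptions, not in the documents: the 5% null is a confirmed rate; a share f of true non-responders records one unconfirmed PR; all true responders are counted. The counted null rate is then 0.05 + 0.95f.

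| f | Counted null rate | P(declare active) |
|---|---|---|
| 0 | 0.0500 | 0.080 |
| 1% | 0.0595 | 0.120 |
| 2% | 0.0690 | 0.165 |
| 3% | 0.0785 | 0.215 |
| 5% | 0.0975 | 0.322 |

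The 0.10 target is reached at a counted rate of 0.0549, so f = 0.0049/0.95, about 0.5%.

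**5. Errors in the other direction**

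If 10% or 20% of true responders are not counted (f = 0), the rate under the alternative is 0.18 or 0.16, and power is 0.737 or 0.656. If f = 1% and 20% of true responders are missed, the counted null rate is 0.8 × 0.05 + 0.95 × 0.01 = 0.0495 and the false-positive probability is 0.079, about the stated value. The net effect depends on rates the plan does not give.

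**The case against.** The case against has several parts, most of which stand.

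- **The RECIST 1.1 rules are not in the documents**; the guideline is only listed as a reference. A reader might infer that Section 11 departs from it on nodal measurement, an absolute growth minimum or MRI thresholds, and so that the primary endpoint is not the one stated. That cannot be established here. What the documents show is a named version beside unversioned rules that conflict among themselves.
- **The 20 mm threshold is not the whole rule.** Spiral CT at 10 mm is in the same sentence. Section 11.1.1 may also be meant as the working definition behind 4.1.6, in which case the 14 mm MRI patient is ineligible rather than an unavoidable non-responder. Either reading is possible, which is why the text needs settling.
- **One 10 mm target is an extreme case.** Section 11.1.3 takes the largest lesions, up to five, and 4.1.9 requires multiple metastatic sites. No frequency can be derived. Section 11.0 also lets asymptomatic patients continue to the next scan to confirm progression, so PD does not end treatment automatically.
- **The waiver in SAP 7.1 is prespecified and explicit.** A reader might call it a contradiction of the protocol, or of the PD confirmation step. It is neither: no protocol text requires CR or PR to be confirmed, and confirming PD where flare is suspected serves another purpose.
- **The error rates are assumed.** If 5% is already an unconfirmed rate, 0.080 stands.

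None of this removes the conflict in 11.1.1, the misdirected footnote or the undefined null.

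**Conclusion.** The concern holds as a matter of specification. Section 11 needs one RECIST version, one threshold per imaging method and a working cross-reference, and the plan must say what kind of response its 5% null describes. The PD rule matters mainly for CBR, DOR and treatment continuation, and for ORR only when small growth comes before a response.

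The figures of 0.12 to 0.32 for the false-positive probability are a sensitivity range. They rest on f of 1% to 5% and on a confirmed null. They show that the 3-of-21 rule has little slack, with the 0.10 target passed at f of about 0.5%; they do not show that the trial's error rate is inflated. The stronger statement, that responses and progressions are misclassified, has no rate behind it. The most the documents support is that responses may be overcounted, with the net direction unknown once the other rules are included.

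**What to change.** **Protocol Section 11.** State that RECIST 1.1 governs. Replace the measurability, sum and PD definitions in 11.1–11.2 with those of the cited guideline, checked against it, or list each intended deviation. Give one threshold per imaging method. Point the Table 8 footnote to 11.0, and reconcile the two: the footnote makes confirmation mandatory for new lesions or flare, while 11.0 permits asymptomatic patients to continue until confirmation. Because 8.2.2 ties durvalumab to progression, those passages must also agree; which rule applies is the sponsor's clinical decision.

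**SAP 7.1.** Keep the prespecified unconfirmed ORR and the 3-of-21 rule. State whether the 5% null is a confirmed or an unconfirmed rate. Add confirmed ORR, meaning CR or PR still present at the next scheduled scan, as a sensitivity analysis, and report whether 3 responses are reached on that count.

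**Cost.** The SAP is marked as a draft, diameters are recorded in millimetres, and the 8-weekly scans are already planned. Some existing images may need re-reading. The confirmed rate may be lower, and responders who stop early may lack a confirming scan because the follow-up column of Table 2 has no tumour measurement. If 10% or 20% of true responders go unconfirmed, power on the confirmed count is 0.74 or 0.66 instead of 0.80, which is a reason to keep it as a sensitivity analysis.

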12.0 PATIENT ENTRY PROCEDURES

12.1 Patient consent form

Before study entry, the consent form including any addenda, must be signed and dated by the patient and the person obtaining informed consent. **In addition, before study entry, a copy of the signed and dated consent form must be forwarded to DSSM. All patient signatures (except initials of first, middle, and last names) should be expunged prior to submission.**

12.2 Study entry

DSSM will verify that the research site has current IRB approval for the study. Entry will not take place if the IRB approval is not current with IRB oversight responsibility.

All patients must be enrolled through DSSM. Once the entry eCRFs have begun to be entered, submit copies of the redacted signed consent form, and supporting documents to

The entry material must be received by DSSM **no later than 4:00 p.m. Eastern Time, Monday through Friday, excluding holidays**. Once received the review process will begin. When the review is complete and approved, an enrollment confirmation will be sent. **This process could involve some unavoidable delays. Therefore, it is necessary to plan adequate time (at least 24 hours) between study entry and the initiation of the patient's study therapy.**

12.3 Patient study number and treatment assignment

After all the entry materials have been reviewed and approved, the institution will receive the following via e-mail:

- confirmation of registration and study entry;
- Patient Identification number.

12.4 Investigator-initiated discontinuation of study therapy

In addition to the conditions outlined in the protocol, the investigator may require a patient to discontinue study therapy if one of the following occurs:

- the patient develops a serious side effect that cannot be tolerated or that cannot be controlled with other medications,
- the patient's health gets worse,
- the patient is unable to meet the study requirements, or
- new information about the study drugs or other treatments for colon cancer becomes available.

If study therapy is stopped, study data and other materials should be submitted according to the study schedule unless the patient withdraws consent from the study or until there is a diagnosis of a secondary malignancy.

12.5 Patient-initiated discontinuation of study therapy

Even after a patient agrees to take part in this study, the patient may stop study therapy at any time. If study therapy is stopped, no new therapy begins and the patient still allows the study doctor to submit information, study data and other materials should be submitted according to the study schedule ([Table 2](#)).

12.6 **Patient-initiated withdrawal from the study**

If a patient chooses to have no further interaction regarding the study, the investigator must provide DSSM with written documentation of the patient's decision to fully withdraw from the study. Any data collected up to the time of withdrawal from the study will continue to be used.

13.0 **DATA HANDLING AND RECORDKEEPING**

Refer to the "FC-9 eCRF Completion Guidelines" for detailed instructions regarding data collection, AE reporting, and electronic case report form completion.

